7.2 Description of Interventions/Comparators

We are testing two delivery strategies of CBT for youth anxiety disorders. CBT is the “gold standard” for the treatment of anxiety and is currently used as the standard of care by therapists at all our participating sites. This research does not change the current standard of care used by our sites – it expands the mode used to deliver standard of care by providing therapists training on the evidence-based Cool Kids framework (i.e. a standardized version of CBT).

Specifically, the Kids FACE FEARS trial tested two CBT delivery strategies for pediatric anxiety: (1) Therapist-Led CBT (telehealth, office-based, or hybrid), and (2) Guided Online CBT (with minimal therapist support).

Comparator 1: Therapist-Led CBT for Youth Anxiety (telehealth, office-based, or hybrid).

An extensive body of controlled studies supports Therapist-Led CBT for anxious youth and their families, with therapist-led CBT conventionally considered a “gold standard” psychological treatment for anxious youth.^{31–34} Therapist-Led CBT has traditionally entailed office-based care in which a therapist directly trains youth (and often caregivers) in anxiety management skills then guides children in planning and participating in graded exposure tasks in which they approach increasingly feared situations. In the landmark Child/Adolescent Anxiety Multimodal Study (CAMS) trial, roughly 60% of youth treated with therapist-led CBT classified as “treatment responders” by masked IEs.³⁴ In more recent years, telehealth formats of Therapist-Led CBT for youth anxiety have received considerable and comparable research support.^{47–50}

Although a number of established and highly overlapping Therapist-Led CBTs for youth anxiety exist, the well-supported *Cool Kids* CBT suite for youth anxiety^{99,100} was selected for several important reasons. First, *Cool Kids* includes all the “gold standard” CBT components for treating youth anxiety and has an extensive research base.^{101–103} Second, *Cool Kids* is a time-limited and relatively brief suite of treatment programs delivered across roughly 3 months, which accommodated the PFAC and stakeholder advisor suggestion for relatively short-term treatment. Third, the *Cool Kids* suite of treatment programs comprehensively includes developmentally tailored versions for the full age range of youth included in the study (7–18 years). Fourth, the *Cool Kids* treatment suite has a documented history of successful implementation when rolled out on large-scale levels.^{103,104} Fifth, a parallel self-administered online version of *Cool Kids* teaches youth the same anxiety management skills as the therapist-led version, and in a roughly comparable number of sessions/modules, thus allowing for well-matched and time-equitable comparisons. And finally, the *Cool Kids* therapist-led and online treatment programs are all available in English and in Spanish.

The standard *Therapist-Led Cool Kids Therapy for Anxiety (ages 7-12)*⁹⁹ is a structured, evidence-based, 10-session program for treating youth anxiety in middle childhood and entails ten 50-minute weekly sessions with children and families. Therapists teach youth and caregivers core CBT components including anxiety psychoeducation, cognitive/coping skills for thinking more realistically and adaptively, problem-solving skills, and graded exposures to anxiety provoking situations. Caregivers and youth are taught skills for managing anxiety and for reducing avoidant behaviors. Caregivers are included in all sessions (adjusted developmentally) and are taught parenting skills plus personal anxiety management. The program is supported by

a structured therapist manual and with developmentally tailored child and parent workbooks. *Cool Kids* is available in many languages, including English and Spanish, and has been adapted slightly for different age groups. The *Therapist-Led Chilled Therapy for Anxiety* (ages 13-18 years) is an adolescent version of *Cool Kids* and includes a workbook geared specifically for adolescents; in this version teens take a more central role in managing their anxiety, and caregivers do not participate in all of the sessions. This version also includes ten sessions.

Comparator 2: Guided Online CBT for Youth Anxiety (With Minimal Therapist Support).

To expand the accessibility and reach of CBT for anxious youth, a suite of self-paced, online, multimedia, CBT-based programs for youth anxiety was developed to run parallel to the therapist-led *Cool Kids* program. This online suite of programs covers identical content in a largely self-administered format. Similar to Therapist-Led *Cool Kids*, the *Cool Kids Online* suite of programs is comprised of separate developmentally tailored online programs, two of which were used in the present trial, depending on the age of the child: (1) “Cool Kids Online” for ages 7-12 years, and (2) “Chilled Out” for youth ages 13-18.^{54,105,106} These programs consist of 8 modules that are to be completed on a roughly weekly basis allowing for well-matched and time-equitable comparisons to the Therapist-Led CBT comparator. The online programs have already been used in numerous countries and are available in multiple languages, including Spanish. The programs include the same core CBT components as the Therapist-Led *Cool Kids* programs, feature interactive, engaging formats, and include video and audio clip examples of how to implement skills. In Cool Kids Online, caregivers take on the role of their child’s coach, helping them put their skills into practice, and learn helpful ways of responding to their child’s anxiety. In the Chilled Out adolescent online version, the teen takes primary responsibility for program completion, and there are features designed to specifically increase teen engagement—e.g., there are real teens featured in the videos, teens demonstrate skills for managing anxiety, and there is a “playlist” menu where teens can choose to re-visit content and cover skills at their own pace. The programs were originally developed in Australia. For both Cool Kids Online and Chilled Out, “Americanized” versions of the programs were used that include videos with diverse representation (e.g., American children, families, and experts; broader representation of individuals of color; removed Australian accents or vernacular).

To foster supportive accountability and engagement,^{67,68} families in this condition receive brief phone check-in calls (i.e., < 15 minutes) from a therapist every other week. To ensure these brief calls do not drift into treatment sessions, therapists work from a conversation guideline to standardize calls (with space for flexibility as appropriate). Therapists should begin each check-in call with an explanation of the purpose of the call—i.e., to see how their use of the online modules is going, to find out whether the child/teen/caregiver has any questions, to support the family with the program, and to make a plan for continued practice. Therapists then check in briefly about each of the following components: (a) engagement with online program and activity completion (“Were you able to log into the online program? If not, what got in the way?”); (b)

identification of current difficulties/barriers, including technical or motivational challenges (“Did anything get in the way of completing activities or practice? Did you experience any difficulties as a parent with respect to your child/teen’s anxiety management?”); (c) brainstorming possible solutions to identified barriers (“Let’s see if we can problem-solve together and come up with some solutions to help you complete materials this week”); (d) review of anxiety and caregiver progress (“Has your/your child’s level of anxiety changed since beginning the program?); (e) technical questions about content (“Do you have any specific questions about the material that you learned in the modules you completed?”); (f) assignment/plan for next two weeks, providing encouragement and praise for even small successes; and (g) confirmation of the next call.

Of note, the comparators included across the two treatment delivery strategies cover identical therapeutic content, although the therapist-led CBT program entails slightly more sessions than there are modules in the self-administered CBT program in order to afford opportunities for alliance building. At the same time, participants in the self-administered online CBT program are able to revisit various modules multiple times. It is believed that the additional number of sessions in the therapist-led CBT program is roughly offset by the opportunity for those in the self-administered CBT program to revisit modules multiple times. In addition to the two comparators offering identical therapeutic content, participants across the two delivery strategies will be given the identical amount of time (i.e., up to 20 weeks) within which to complete their course of treatment, further ensuring equipoise across comparators.

7.3 Implementation of Cool Kids CBT in Pediatric Health Settings

In order to analyze component 1 of the study, therapists, program staff, and research assistants will be asked to complete assessments about organizational factors that serve as barriers or facilitators to implementing the comparators in the real-world context of pediatric primary care and pediatric health settings. Study personnel will have a team meeting with site staff to introduce them to the study and their roles as researchers and participants in the study. Therapists and program staff will be sent consent forms along with their pre-training assessments prior to their on-site Cool Kids CBT training. By completing the pre-training assessments, therapists are indicating that they have read the consent form, that all of their questions have been answered, and that they voluntarily agree to participate the study. Research staff will track which staff were sent consent forms and completed pre-training assessments, and will follow up individually with clinic staff as needed to ensure enrollment into the study before the site training day.

7.4 Evaluating Therapist-Led Cool Kids (office-based or telehealth) vs. Self-Administered Web-based CBT for Child Anxiety

Once therapists at sites are trained in delivering therapist-led Cool Kids CBT, all patients screened positive for elevated anxiety can be offered Cool Kids CBT as standard treatment at

the discretion of their therapist. Those who screen positive for elevated anxiety and choose to enroll in the study will be randomized to receive either the therapist-led Cool Kids (telehealth, office-based, or hybrid) CBT, or the guided online Cool Kids CBT. Participants in the study will be asked to complete assessments throughout their treatment and post-treatment for the purposes of this study. Short-term and longer-term outcomes will be analyzed in both arms to compare both forms of delivering CBT.

7.5 Method of Assignment/Randomization

Participants will be randomized by family. If the participant will be completing the program and enrolling in the study without parental involvement, they will be randomized individually. Each patient/family will receive a unique study ID at the time of referral to the study that is not connected to identifiable data. Before randomization, the referred patient/family will complete the following enrollment procedures: (1) each referred patient will complete a clinical intake at their referral site with a therapist, (2) each referred patient/ family with complete an assessment to determine eligibility for the study, (3) each referred patient/family will give study staff consent to participate in the study, (4) the participants will complete baseline assessment, and (5) the participants will complete the PARS assessment

Once a participant/family gives consent to enroll in the study, they will be provided with a unique ID number and this ID number will be connected to their identifiable data (access to identifiable data will be limited). The clinical intake can happen before or after consent is received, but the baseline assessment and PARS assessment must be completed after the patient gives consent to enroll in the study. Once all four steps of enrollment (consent, clinical intake, baseline assessment, and PARS) are completed, the participant/family will be randomized.

Anticipated participants were divided into 16 strata based on the 16 combinations of 4 regions (Boston, Miami, Baltimore, Seattle), 2 languages (English, Spanish), and 2 age groups (7-12, 13-18). For each strata, a randomized list of conditions (therapist-led treatment versus guided online treatment) was generated at Sealed Envelope using random blocks of size 4. Random blocks help maintain equally sized treatment groups while also reducing bias in random assignment by making it more difficult for researchers to (deliberately or not) predict the next condition. Random assignment lists have been archived with the Data Management team and with [name].

Randomization assignments are made centrally at the FIU data coordination site. Once a participating family's baseline assessments are completed (see Measures), the randomization assignment software is programmed to send an automated push notification revealing their assigned condition simultaneously to the FIU data management team (for data recording purposes) and to the research coordinators and clinical team at the participant's site (to orient the family to their assigned treatment condition).

Each site will create their own workflow for recruitment procedures and submit this to the lead site. Sites will also report their standard of care procedures for delivering the therapist-led program – whether it will be office-based, via telehealth, or a hybrid.

Because of the nature of the intervention, we will not be able to mask study participants, therapists, and RAs from treatment assignment. However, research staff who will be administering the PARS assessment will be masked to study condition.

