7.13 Randomization Procedures

Once a participant has completed all 5 procedures necessary to be randomized, the local RA will complete a randomization form in REDCap to document and confirm that all procedures have been completed. Once all procedures have been documented, the form can be submitted, and the random assignment will be released. Randomization assignments are made centrally at the FIU data coordination site. Families are randomly assigned to one of the two treatment conditions by randomization software programmed to stratify assignments by Site (Baltimore, Boston, Miami, or Seattle), Language of Treatment (English or Spanish), and Age (7-12 years or 13-18 years). An automated push notification is sent that reveals the family's assigned condition simultaneously to the FIU data management team (for data recording purposes) and to the research coordinators and clinical team at the participant's site (to orient the family to their assigned treatment condition). The local RA will report the result to their clinical team and to the participant.

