7.15.4 Retention and Study Compensation

Based on similar studies conducted in usual care settings that do not provide free study treatment, we expect roughly 30-50% attrition by the final follow-up timepoint, and roughly 10% of data points to be missing with each collected timepoint. REDCap surveys will be configured to minimize missing values (e.g., requiring participants to complete each item, or explicitly indicate “refuse to answer” before proceeding to the next item; providing real time alerts to the data management team when items or entire forms are missing). Data will additionally be checked on a weekly basis by a research supervisor, and patterns of missingness will be identified and corrected in real time throughout the study. To further reduce instances of missing data, we have kept the number of study forms to a minimum in order to minimize the burden to participants, and participants will be provided compensation for their time completing study forms. Finally, participants will be compensated for the burdens of completing study assessments (see below).

Given the aim to evaluate treatment engagement and performance under typical circumstances, families are not compensated for participating in treatment. To ensure generalizability and observe the treatment comparators under natural conditions, treatment is not funded by the study nor offered for free. Rather, treatment is to be paid for via the natural channels of payment in the participating health centers (e.g., insurance and co-payments). In contrast, families are compensated for participation in study assessments that are not part of the treatment comparators under study. Specifically, families will receive the following compensations for completing various study assessment components:

- a. \$50 for baseline assessment (staggered payments: \$25 following baseline questionnaires and \$25 following baseline PARS completion)
- b. \$25 for midtreatment assessment
- c. \$50 for posttreatment assessment
 - i. \$30 additional compensation for completing posttreatment PARS assessment
- d. \$100 for completing follow-up assessment

*Coaches (who are not guardians) will not receive compensation for the assessments they complete. Compensation will only be provided to the youth and guardian informants. One ClinCard that will be loaded with the above payments will be given to each family for each child enrolled in the study.

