7.16.3 Covariates

Covariates for each model will include site, language of care, youth age, youth gender, youth race, youth ethnicity, and family resource insecurity (see Measures)

7.16.4 Primary analyses: Comparative effectiveness analyses. For primary analyses on continuous outcomes that were measured across the 4 major timepoints (e.g., caregiver- and youth-reports on the PROMIS Anxiety Scale, CALIS), mixed models of change¹⁴⁴ will be run separately for each outcome. Mixed models are preferred for longitudinal designs because they allow for individual estimates of change and have robust power in the presence of missing data and attrition.^{145,146} Covariates for each model will include site, language of care, youth age, youth gender, youth race, youth ethnicity, and family resource insecurity (see Measures), and any other baseline variables found to significantly differ across participants in the two conditions. The random effects of intercept (reflecting individual variation in mean outcome level) will be assessed. The fixed effects of Treatment Condition, Time, and the Treatment \times Time interaction will be analyzed in the prediction of change. We will examine non-linear models of change (i.e., log transformations of Time), which afford examination of symptom trajectories across time that are not gradual and incremental (e.g., steep improvements during initial weeks of treatment, followed by a slowing down of improvements toward the end of treatment, and then relative stability across the follow-up time interval). To aid interpretation of the meaningfulness of between-group differences, Cohen's d 's will be computed for each continuous outcome on model means at post and follow-up.

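### The plan assigns by family within child-age strata and allows for several children per family, but gives no rule for assigning a second sibling and no family term in any model

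*Combined protocol and SAP*

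**What the plan says.** - **Unit.** Section 7.5: "Participants will be randomized by family". A youth who takes part without a parent is randomized individually. Section 7.13 agrees on the unit: "Families are randomly assigned to one of the two treatment conditions by randomization software programmed to stratify assignments by Site", followed by language of treatment and age.
- **Strata.** Section 7.5 crosses four regions with language and age band to form 16 lists, generated "using random blocks of size 4". The age bands are 7-12 and 13-18, so they describe a child.
- **Siblings.** Section 7.15.4 says one payment card is "given to each family for each child enrolled in the study". Section 6.3.2 has no criterion restricting a family to one child.
- **Release.** Under 7.5 and 7.13 the assigned condition goes to the site's coordinators and clinical team. Section 7.5 says that participants, therapists and research assistants are not masked.
- **Analysis.** Section 7.16.1 names two sources of clustering: repeated measures within a child, and children within a site. For the mixed models, 7.16.4 says: "The random effects of intercept (reflecting individual variation in mean outcome level) will be assessed". The logistic and linear models in the same section have no cluster term. Site enters as a covariate. Family appears in none of them.

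**The concern.** The unit of assignment and a stratification factor sit at different levels, and nothing connects them when two siblings enrol. Take siblings aged 10 and 15. The plan can be carried out in two ways, and each has a cost.

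- **The second child takes the family's arm.** If that child enrols later, the arm is already known to the household and the site. Final eligibility rests on the baseline PROMIS, where one positive informant is enough (7.10.1), and for a child under 13 only the caregiver's baseline form is required (7.11). So the person whose answers decide entry could know the arm. The 15-year-old's assignment would also not come from the list for that age band.
- **Each child is drawn from the list for that child's age.** Siblings can then land in different arms. One caregiver might attend therapist-led sessions for one child and act as coach in the online program for the other (7.2), which blurs the contrast within that household.

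Under either practice, the analysis treats as independent children who share a home and often a caregiver informant. Because 7.16.2.4 keeps every randomized participant in the analysis, any such child stays in all primary models.

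**Working it through.** **The plan's own clustering figure.** Section 7.16.1 uses 1 + (m - 1) × ICC with m = 4 and ICC = 0.5. This gives 1 + 3 × 0.5 = 2.5, then 60 × 2.5 = 150 per group and 300 in all. These steps reproduce. The starting value of 60 does not follow from the printed formula, which has no effect size; that is a separate matter and nothing below depends on it. The design effect covers the four measurements on a child and has no component for siblings.

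**Inputs for the sibling effect.** The documents give neither the share of children in sibling pairs (s) nor the correlation between siblings (ρ). Both are assumptions: s = 5-15% and ρ = 0.3-0.5, with a wider range of s = 2-20% and ρ = 0.2-0.6.

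**Formula.** Take a difference in means between two arms of 150. The variance under independence is 2σ²/150. The number of pairs is 300s/2 = 150s. Each pair contributes 2ρσ²/150², added if the siblings share an arm and subtracted if they are split. Relative to independence:

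- all pairs in the same arm: 1 + sρ
- all pairs split: 1 - sρ
- a proportion p in the same arm: 1 + sρ(2p - 1), which is 1 when p = 0.5

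**Same-arm pairs** (true two-sided alpha = 2 × [1 - Φ(1.96/√DE)]):

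| s | ρ | DE = 1 + sρ | √DE | True alpha at nominal 0.05 | Effective N = 300/DE |
|---|---|---|---|---|---|
| 2% | 0.2 | 1.004 | 1.002 | 0.0505 | 299 |
| 5% | 0.3 | 1.015 | 1.007 | 0.0517 | 296 |
| 10% | 0.4 | 1.040 | 1.020 | 0.0546 | 288 |
| 15% | 0.5 | 1.075 | 1.037 | 0.0587 | 279 |
| 20% | 0.6 | 1.120 | 1.058 | 0.0640 | 268 |

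Over the main range, the correct standard error is 0.7% to 3.7% larger than the one reported.

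**Split pairs.** The factor runs from 1 - 0.05 × 0.3 = 0.985 to 1 - 0.15 × 0.5 = 0.925. The square roots are 0.992 and 0.962, so the correct standard error is 0.8% to 3.8% smaller than the one reported. With separate draws, some pairs would share an arm and others would be split, and the two errors would partly offset.

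**Scope of the formula.** It fits outcomes compared at one time point, such as posttreatment satisfaction, and approximately the PARS responder analysis. For the treatment-by-time term in the mixed models, the relevant ρ is the sibling correlation in change, which is also not given.

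**Children who could enter with a known arm.** The number of second siblings is 300s/2, or 7.5 to 22.5 for s = 5-15%: about 8 to 23 children. This is a ceiling. It is reached only if every second sibling enrols after the family's assignment is released and takes that assignment.

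**The case against.** The strongest reply is that *family* here means one caregiver and one child. The sentence after the rule in 7.5 contrasts a family with a youth taking part without a parent, not a household with its separate children. Section 7.11 describes a family as a parent and a child and sets the randomization requirement by that child's age. On this reading each unit has one age, the strata fit, and each sibling is drawn separately. The payment sentence in 7.15.4 is compatible with that, since it says nothing about assignment. Enrolment detail may also sit in the Manual of Procedures, which is not among the documents.

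This stands as a possible reading, and it rules out some stronger conclusions. A reader might infer that every second sibling enters with a known arm drawn from the wrong stratum. The documents do not support that:

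- No section says that a sibling inherits an arm.
- A known arm requires both inheritance and later enrolment. Section 7.5 releases an assignment once the family's baseline is complete, which could cover siblings who enrol together.
- A wrong list also requires siblings in different age bands or languages.
- Split arms and inherited arms are alternatives, so their harms do not add up.

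Nor can one say that standard errors are always too small; with split siblings the error tends to go the other way.

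The reply does not remove the gap. The caregiver-child reading has to be inferred, it allows split households, and it still leaves siblings without a family term.

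**Conclusion.** The point holds as an unspecified sibling rule combined with an analysis that ignores the unit the plan says it randomizes. That more than one child per family may enrol rests on the payment sentence in 7.15.4 and the absence of a bar in 6.3.2; how many do so is unknown. If 5-15% of children are in sibling pairs with correlation 0.3-0.5, standard errors should be about 0.7-3.7% larger for same-arm pairs, and they tend to be too large already for split pairs. That would rarely change a conclusion. The more important issue is allocation concealment for any sibling who enrols later and takes a known arm, a conditional risk affecting at most about 8 to 23 children under the same assumptions. The change is worth making because it is cheap and the analysis part still works after enrolment has ended. If no siblings enrolled, one sentence saying so closes the point.

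**What to change.** 1. **Section 7.5.** State that when siblings enrol together, all of them complete consent, the baseline PROMIS and the baseline PARS before a single family assignment is released. Draw it from the age stratum of a named index child, and say how the index child is chosen. State also how a sibling who presents after release is handled.
2. **Section 7.16.4.** Use family-clustered (cluster-robust) standard errors in the mixed, logistic and linear models, or a family random intercept where it can be estimated.
3. **Reporting.** Give the number of sibling sets, and how many share an arm or are split.
4. **Sensitivity analysis.** Repeat the primary models with one index child per family. This also removes any sibling who entered with a known arm.

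Barring siblings from enrolment is not needed.

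Cost: a release rule in REDCap, a short wait for a second sibling's baseline, and a variance option in the models, applied in each imputed data set before pooling. With few pairs, a family variance may be poorly estimated or hard to separate from the child intercept, and the multilevel imputation in 7.16.2.2 would have to match it. Clustered standard errors with the index-child analysis are therefore preferred to relying on a family random intercept.

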
Secondary and Exploratory Outcome Variables
 
Treatment engagement and barriers, broader youth psychopathology (i.e., internalizing problems, externalizing problems, and attention problems), youth sleep difficulties, caregiver internalizing symptoms (i.e., depression symptoms, anxiety symptoms, and stress symptoms), and therapist perceptions of treatment response. Other secondary analyses will examine predictors and moderators of differential outcomes, including: demographic factors, clinical factors, caregiver and youth attitudes, and language of care (English versus Spanish), among other factors.

Study Duration
 
The study project has a duration of 5 years.

Study Design

The study design entails a large-scale, streamlined, pragmatic Randomized Controlled Trial (RCT), in which eligible anxious youth presenting to pediatric health care settings will be randomly assigned to receive therapist-led (telehealth, office-based, or hybrid care) versus guided online CBT for youth anxiety and monitored for up to 1 year.

Intervention

Cognitive Behavior Therapy (CBT) is a well-supported standard of care for the treatment of anxiety in children and adolescents. This study is a pragmatic comparative effectiveness design comparing two modalities for administering CBT: Therapist-led CBT (telehealth, office-based, or hybrid care) vs. Guided Online CBT (with minimal therapist involvement).

Study Population

We will include youth ages 7-18 years of age presenting to pediatric health care sites, including community health centers serving primarily low-income and traditionally underserved populations, affiliated with four major academic medical centers, each distinguished by renowned programs in behavioral health integration: Boston Medical Center in Boston, MA; Nicklaus Children's Hospital in Miami, FL; John's Hopkins Hospital in Baltimore, MD, and Seattle Children's Hospital in Seattle, WA.

Number of Participants

We require 150 participants per treatment group, for a total of 300 participants.

Abbreviations

Abbreviation	Explanation
ADHD	Attention-deficit/hyperactivity disorder
AHRQ	Agency for Healthcare Research and Quality
BMC	Boston Medical Center
BUMC	Boston University Medical Campus
CALIS	Child Anxiety Life Interference Scale
CBT	Cognitive Behavioral Therapy
CCF	Center for Children and Families
CRF	Case Report Form
DE	Design Effect
FIML	Full information maximum likelihood
FISMA	Federal Information Security Management Act

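### Fixed blocks of 4 make the next assignment easier to predict, not harder as Section 7.5 says: up to about a third can be certain to someone who knows the block size and sees a whole stratum

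*Combined protocol and SAP*

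**What the plan says.** Section 7.5 has anticipated participants "divided into 16 strata based on the 16 combinations of 4 regions", two languages and two age groups. Each stratum has its own list, generated "using random blocks of size 4". No second size is given, and no step to keep the size from sites is described. The section says the blocks keep the groups equal and reduce bias by "making it more difficult for researchers to (deliberately or not) predict the next condition".

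Section 7.13 repeats the stratification, with software set to "stratify assignments by Site (Baltimore, Boston, Miami, or Seattle), Language of Treatment (English or Spanish), and Age (7-12 years or 13-18 years"). Every stratum therefore lies inside one of the four regions.

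On who sees the results, Section 7.5 sends each assignment automatically to the data management team and "to the research coordinators and clinical team at the participant's site". It also states that "we will not be able to mask study participants, therapists, and RAs from treatment assignment"; only the PARS raters are masked.

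On who acts before randomization:
- The local RA completes the eligibility screening form (Section 7.10.1).
- A site therapist judges at intake whether outpatient CBT is the appropriate level of care (Section 7.12).
- Once all steps are done, "the local RA will complete a randomization form in REDCap", and submitting it releases the assignment (Section 7.13).
- Section 7.10.1, by contrast, describes randomization as starting automatically once the steps are complete.

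**The concern.** By naming predictability as a source of bias, the plan accepts that it matters. Central assignment conceals the list, but it does not conceal the assignments already made. Under a fixed block size, those earlier assignments progressively reveal the rest of the block.

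Unmasked staff at the participant's site receive the results, and people in the same roles screen families, judge suitability and submit the form. Someone who expects a particular arm could hurry, delay or discourage a particular family. The arms would then differ in who enters them, which is what randomization is meant to prevent. Such a difference need not appear in any measured baseline variable.

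**Working it through.** The documents give no predictability figure. Their own figure here is the number of strata, and it reproduces: 4 regions × 2 languages × 2 age groups = 16.

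**Inputs.** Block size 4 (Section 7.5). Allocation 1:1, from the Synopsis: "We require 150 participants per treatment group, for a total of 300 participants". Each block therefore holds 2 + 2. The mean stratum size is 300/16 = 18.75 families.

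**Complete blocks.** There are C(4,2) = 6 equally likely orders of AABB, hence 6 × 4 = 24 positions. A position is certain if one arm is already used up in the block. The best-guess rate is the mean of max(A left, B left)/(total left).

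| Position in block | Probability certain | Best guess right |
|---|---|---|
| 1 | 0 | 1/2 |
| 2 | 0 | 2/3 |
| 3 | 1/3 | 2/3 |
| 4 | 1 | 1 |
| Mean | (4/3)/4 = 8/24 = 33.3% | (17/6)/4 = 17/24 = 70.8% |

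Simple randomization would give 0% certain and 50% guessed.

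**Incomplete last blocks.** The 300 families were spread at random over the 16 strata, with regions and age groups equal and the Spanish share assumed at 10%, 30% or 50%, because the documents give no split. In every case the mean certain share was about 31% (simulated range 30% to 33%) and the best-guess rate about 70%.

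As a hand check, a stratum of 19 has four complete blocks plus three positions:
- Certain: (4 × 4/3 + 1/3)/19 = 5.67/19 = 29.8%.
- Best guess: (4 × 17/6 + 1/2 + 2/3 + 2/3)/19 = 13.17/19 = 69.3%.

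**Alternatives.** These were simulated with 19 families per stratum and an observer who knows the set of sizes but not their order.

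| Block sizes | Certain | Best guess right |
|---|---|---|
| 4 only | about 30% | 69% |
| 4 and 6, random | about 6% | 68% |
| 4, 6 and 8, random | about 2% | 66% |

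A larger fixed size helps less: in complete blocks, 25% of assignments are certain with size 6 and 20% with size 8.

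**The case against.** *The sentence may be read charitably.* Randomly permuted blocks are harder to predict than strict alternation. That is true, but Section 7.5 does not name that comparison, and against simple randomization the sentence is wrong. Nor can the wording mean varying sizes, since only one is given.

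*One third is a ceiling.* A reader might infer that site staff know a third of assignments in advance. The documents do not support that. It requires someone who knows the block size, sees a whole stratum in order and keeps count across interleaved strata. Strata are regional, notices go to the team at the participant's site, and the regions include affiliated community health centers. How results are shared between clinics is not stated, nor whether the version sites held during enrolment printed the block size. This objection stands.

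*Discretion is narrow.* Final eligibility rests on a PROMIS threshold, Section 7.11 sets follow-up periods for baseline completion, and Section 7.10.1 calls the release automatic. Intake may precede consent, so other families may be randomized in the stratum before this one. Much of this stands. Even so, Section 7.13 makes release depend on a form the RA submits, and the clinician's judgement at intake remains.

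*Later safeguards exist.* A reader might infer that nothing downstream could correct such selection. That is too strong. Section 7.16.4 adjusts for site, language, age, gender, race, ethnicity and resource insecurity, and for other baseline variables that differ significantly between arms. PARS response is relative to each child's own baseline, and its raters are masked. Adjustment nevertheless deals only in part with measured imbalance and not at all with unmeasured selection. Masked rating protects the rating, not the composition of the arms.

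*Small blocks are defensible.* With under 19 families per stratum on average, they protect balance. This stands. The difficulty is a single size combined with the claim made for it.

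*No motive is shown.* The same therapists serve both arms (Section 7.7). The arms do differ in therapist time, with ten 50-minute sessions against calls of under 15 minutes every other week, but the documents do not show that anyone would act on that.

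**Conclusion.** The statement about predictability in Section 7.5 is incorrect relative to simple randomization. With a fixed block size of 4, up to about one third of assignments (33% in complete blocks, about 31% with incomplete last blocks) are certain, and the best guess is right about 70% of the time. Both figures assume an observer who knows the block size and sees all earlier assignments in the stratum; with a partial view, less can be predicted.

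Because unmasked site staff receive results and carry out the steps before randomization, some room for selection exists, within the limits set out above. This is a vulnerability, not evidence that assignments were steered. It is a correctable design weakness together with a misstatement, and it does not by itself invalidate the comparison.

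**What to change.** The text mixes past and future tense and does not say whether enrolment is closed, so the action depends on that.

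**If enrolment continues.** Regenerate the unused part of each of the 16 lists with block sizes varied at random, for example 4 and 6. Keep the sizes at the coordinating centre and out of documents that sites hold. The gain is mainly the loss of certainty (about 30% to 6%); the best-guess rate hardly moves (69% to 68%). The cost is new lists, a change to Section 7.5 and slightly larger possible imbalance in small strata: an unfinished block can leave the arms up to 3 apart with size 6, against 2 with size 4.

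**If enrolment is complete.** Correct the sentence in Section 7.5 so that it no longer claims unpredictability. Add a check to the SAP: for each family, compute the probability of Therapist-Led CBT given the earlier assignments in its block (0, 1/3, 1/2, 2/3 or 1), then relate baseline PROMIS and PARS to that probability within stratum. Without selection, no association is expected. The data are already collected, so the cost is one descriptive analysis. A null result would not exclude selection on unmeasured features, and the report should say so.
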